In recent years, various international consensuses have brought these fundamental concepts to the clinical practice. The European Working Group on Sarcopenia in Older People (EWGSOP) developed a practical clinical definition and consensus diagnostic criteria for age-related sarcopenia, recommending the use of the presence of both low muscle mass and low muscle function (strength or performance) for diagnosis. Recently, a new consensus (EWGSOP2) recommended low muscle strength as the primary parameter to assess sarcopenia and new

[figure not shown]
cut-off points to increase harmonization of sarcopenia studies (15).

Given the above, there is an ongoing intensive search for novel therapies, including dietary ones that can attenuate the loss of muscle mass and strength in the elderly (10, 16). Interestingly, a growing body of research indicate that nutritional factors can preserve muscle function from age-related decline. In particular, phenolic compounds, widely distributed in fruits including grapes, have shown beneficial effects in muscle health (17, 18). Phenolic compounds have garnered attention because they ability to alleviate disease pathologies through anti-inflammatory, anti-carcinogenic and antioxidant

properties. However, the exact influence of grapes and grapes phenolic compounds mitigating sarcopenia in humans remains unexplored.

A novel and understudied mechanism by which skeletal muscle might mediate their protective effect against sarcopenia is by secreting myokines. Irisin is a myokine regulated by peroxisome proliferator-activated receptor gamma co-activator-1 α (PGC-1 α) and released into the bloodstream after cleavage of the Fibronectin type III domain-containing protein 5 (FNDC5) (**Fig 1.**). Recent studies have indicated that circulating irisin can promote skeletal muscle growth (12, 19, 20). Lower irisin concentrations have been observed in sarcopenia patients (21) and dialyzed patients with cardiovascular disease (22). Furthermore, lower irisin plasma levels are associated with sarcopenia in postmenopausal women (10).

In a recent study, we have shown that phenolic compounds present in a grape pomace extract (GPE), prevent irisin downregulation in rats fed a high-fat diet and in L6 myotube cells. In particular, we documented that consumption of the GPE activates the FNDC5/irisin pathway, with a significant increase of PGC-1 α and FNDC5 protein

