levels compared to control and high fat diet groups (**Figure 2A-B**). Furthermore, supplementation with GPE led to the increase in irisin plasma level (**Figure 2C**)(11).

In order to understand the underlying mechanism involved in the GPE-related irisin increased levels, we next evaluated the effects of epicatechin, one of the main flavonoids present in GPE, in L6 myotubes challenged with palmitate, to mimic a condition of fatty acids oversupply. Protein levels of PGC- 1 α and FNDC5 were significantly higher in the EC and palmitate-treated cells, compared with palmitate-treated cells (**Figure 3A-B**). The same tendency was observed by immunocytochemical analysis of PGC-1 α , while no differences were observed in FNDC5 fluorescence intensity among treatments (**Figure 3D-E**). In addition, EC induced a 2-fold increase in irisin levels secreted to the medium compared with cells treated with only palmitate (**Figure 3C**). These data strongly indicate that phenolic compounds enhance irisin levels in vitro and in vivo.

These intriguing data allow us to hypothesize that phenolic compounds present in grapes might have a positive effect in human health, specially preventing sarcopenia in elderly humans, in part, by increasing irisin levels.

4) Enrollment Numbers

We chose the “changes in plasma irisin levels” as our primary outcome to determine the power calculations for sample size. Based on our preliminary data (11), 5 individuals per group are required to reach 80% power to detect differences in irisin levels between the groups, at a $\alpha=0.05$, using a two-sided paired T-test. We propose to enroll 7 individuals per group, instead of 5, in the event of a patient drop out of the study (for any unforeseen circumstances). In total we will have 14 subjects.

5) Inclusion and Exclusion Criteria

Inclusion Criteria: postmenopausal women aged 60 years or older with a hand-grip strength media value of 16 kg or lower, normal body mass index (BMI) with values between 18.4 and 24.9 kg/m², blood pressure below 130/80 mmHg, and plasma glucose and cholesterol concentrations below 100 and 200 mg/dl.

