Return stool and urine collection kit			X	X
Adverse events assessment			X	X

After confirmation of the inclusion/exclusion criteria enrolled subjects will be asked to travel to Ragle Human Nutrition Center at University of California Davis for 3 study visits: a baseline visit (**visit 1**), and a 3-week intervention visit (**visit 2**) and a final 6-week visit (**visit 3**)

Visit 1 (baseline visit):

On this visit, baseline measurement will be done. Fasted participants (12 h) will provide blood samples and complete two tests:

Blood samples: from each participant 20 ml of blood will be extracted. The following parameters will be measured in plasma, (the same parameters will be measure in the following visits 2 and 3):

Blood parameter	Volume of blood needed	Visit 1	Visit 2	Visit 3
Irisin	1200 ul	X	X	X
Glucose	1000 ul	X	X	X
Insulin	1200 ul	X	X	X
GLP-1/ 2, GIP	2000 ul	X	X	X
Adiponectin, leptin and ghrelin	3000 ul	X	X	X
Blood urea nitrogen, creatinine	1000 ul	X	X	X
Total cholesterol, triglyceride, high-density lipoprotein (HDL), low-density lipoprotein	2000 ul	X	X	X
Aspartate transaminase, Alanine transaminase	2000 ul	X	X	X
IL-6, IL-15	2000 ul	X	X	X
25-hydroxyvitamin D	1000 ul	X	X	X
Hematocrit	500 ul	X	X	X

Total volume of blood per visit	~ 20 ml	20 ml	20 ml	20 ml
---------------------------------	---------	-------	-------	-------

After taking the blood samples a snack will be provided to the participants in order to complete the following tests.

1. Hand-grip strength: previously described in the screening point
2. Short Physical Performance Battery (SPPB): the SPPB score will be based on three tests, as follows: balance test, gait speed test, and chair stand test (see **Attachment E**). Of note, these tests have been used as a predictive tool for possible disability and can aid in the monitoring of function in older people.

Following, the subjects will randomize into the study supplement: a) Placebo powder (46 g placebo powder in 180 ml of water); or b) freeze-dried table grape powder (46 g grape powder in 180 ml of water). The supplement will be supplied to the participants to complete the following 3 weeks supplementation until the next visit. The investigator or designee will explain the details regarding the preparation and consumption of the supplement [a dosing protocol will be uploaded too (**Attachment F**)].

Also a 24-hs food and physical activity questionnaire will be performed

Briefly, at visit 1:

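### The 80% power claimed for 5 women per group is unsupported for this trial: its only source is rat and cell data, no human effect or SD is given, and the test named does not fit two independent groups

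*Protocol*

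**What the plan says.** **Sizing.** Section 4 (Enrollment Numbers) opens: "We chose the “changes in plasma irisin levels” as our primary outcome to determine the power calculations for sample size". It continues: "Based on our preliminary data (11), 5 individuals per group are required to reach 80% power". Alpha is 0.05 and the test is a two-sided paired t-test. Two women per group are added for dropout, giving 7 per group and 14 in total. No mean difference, SD or standardised effect is stated.

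**The source.** Section 3 (Background) describes the team's own study, in which "phenolic compounds present in a grape pomace extract (GPE), prevent irisin downregulation in rats fed a high-fat diet and in L6 myotube cells". The citation to reference 11 closes the sentence reporting that "supplementation with GPE led to the increase in irisin plasma level". A linked cell experiment used epicatechin: "EC induced a 2-fold increase in irisin levels secreted to the medium compared with cells treated with only palmitate". No SD accompanies either result. The Background also says that what grapes do for sarcopenia in humans has not yet been explored.

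**The trial.** Section 5 admits postmenopausal women aged 60 or older with low grip strength, "normal body mass index (BMI) with values between 18.4 and 24.9 kg/m²", and fasting glucose and cholesterol below 100 and 200 mg/dl. Section 9 randomises each woman to placebo powder or to "freeze-dried table grape powder (46 g grape powder in 180 ml of water". These are two parallel groups.

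**The endpoint.** Section 11 lists hand-grip strength as primary and irisin as secondary. Section 2 calls the study a pilot that is meant to support a larger grant application.

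**The concern.** A power statement needs an effect and a variability that are credible for the people, product and comparison in the trial. Here the only cited source differs in species (rats and cells), in condition (high-fat feeding or palmitate challenge) and in product (pomace extract or epicatechin, not table grape powder). The test named does not match the randomised comparison either. These are separate gaps, and correcting the test would not supply an effect or SD for women.

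The 80% figure is the only quantitative reason given for 14 women. Left unqualified, it tells a reader, or a panel judging the follow-on grant, that the trial's sensitivity for irisin is known when the protocol gives no basis for that.

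**Working it through.** **1. Can the stated figure be reproduced?** No. Section 4 gives n = 5 per group, 80% power and two-sided alpha 0.05, but no effect or SD. The calculation can only be run backwards, to the standardised effect d that n = 5 implies.

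**2. Formulas.** Power is the probability that a noncentral t variable exceeds the two-sided 5% critical value in absolute size.
- Paired: df = n − 1, noncentrality = d√n.
- Two independent groups: df = 2n − 2, noncentrality = d√(n/2), with n per arm.

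**3. Effect implied at 80% power.**

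| n per group | Paired t | Independent t |
|---|---|---|
| 5 | 1.68 SD | 2.02 SD |
| 7 | 1.27 SD | 1.63 SD |

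With a normal approximation, n = 5 would imply 1.25 SD (paired) or 1.77 SD (independent). So the one stated figure is compatible with effects from 1.25 to 2.02 SD, depending on a method that the protocol does not fully describe.

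**4. Carrying the paired effect to the actual design.** Put d = 1.682 into the independent-groups formula:
- 5 per arm: noncentrality 1.682 × √2.5 = 2.66, df = 8, power 65%.
- 7 per arm: noncentrality 1.682 × √3.5 = 3.15, df = 12, power 82%.

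This takes 1.68 to be in units of the SD of one woman's irisin change. If it were instead in units of the SD of a difference between two unrelated women, it would equal 1.682 × √2 = 2.38 individual SDs. That is above 2.02, so 5 per arm would exceed 80%. The protocol does not say which is meant.

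**5. Precision for two independent groups.** The 95% CI half-width in SD units is t(0.975, 2n − 2) × √(2/n):
- 7 per arm: 2.179 × 0.535 = 1.16 SD.
- 5 per arm: 2.306 × 0.632 = 1.46 SD.

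**6. Scenarios.** These effects are assumed; none comes from the documents.

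| Assumed effect | Power, 5 per arm | Power, 7 per arm | n per arm for 80% |
|---|---|---|---|
| 0.5 SD | 11% | 14% | 64 |
| 0.8 SD | 20% | 28% | 26 |
| 1.0 SD | 29% | 41% | 17 |
| 1.5 SD | 55% | 73% | 9 |
| 2.0 SD | 79% | 93% | 6 |

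Step 5 and the independent-t column of step 3 depend only on n and alpha. Step 6 depends on effects that nobody has yet measured in these women.

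**The case against.** The case on the other side has four parts.

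- **It is a pilot.** Section 2 says so, and says that a larger study would follow. Using preclinical data when no human data exist is a legitimate design judgement. This stands as a defence of enrolling 14 women. It does not defend an unqualified 80% claim.
- **There is a biological bridge.** The women are selected for low grip strength, the Background cites lower irisin in sarcopenia, including in postmenopausal women, and it offers a phenolic mechanism. That makes an effect plausible in direction. It supplies neither a size nor an SD.
- **The enrolled number may be adequate.** At 1.68 SD, 7 per arm gives 82% power in independent groups. That is correct if all 14 complete and the effect is that large, and the second condition is the one without support.
- **The numbers do not measure reliance on rat data.** This is right. The gap between 1.68 and 2.02 SD comes from the test, and the low power at 0.5 to 1.0 SD comes from small groups and assumed effects.

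A reader might infer more than the text allows. The protocol does not show that true power is below 80%. It does not state the rats' strain, or which quantities were taken from reference 11 and how they were adapted. Nor does it say that a null irisin result would be taken as proof of no effect.

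**Conclusion.** The point holds as a lack of support. The 80% power statement cites only an animal and cell study of a different grape product, gives no effect or SD in women, and names a test that does not fit two randomised groups. The stronger conclusion, that the trial is underpowered, cannot be drawn: it would need the human effect and SD that are missing.

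What can be said without those inputs is what 14 women deliver for two independent groups. With all 7 per arm, the effect detectable with 80% power is 1.63 SD. If dropout leaves the planned minimum of 5, it is 2.02 SD. These figures assume roughly normal changes, equal variances and a simple comparison of changes. Because the SD of irisin change is unknown, they cannot be turned into irisin units.

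The same sentences also conflict with Section 11 on which outcome is primary, so even a sound irisin calculation would not size the trial for its listed primary endpoint.

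**What to change.** In Section 4:
- Remove the unqualified statement that 5 per group gives 80% power.
- State that 14 women is a pilot size, that no SD of irisin change in women was available, and that the sizing drew on animal and cell data. Do not describe reference 11 as background rationale only, since Section 4 says that it was used for sizing.
- Replace the paired t-test with a comparison of two independent groups, and make the same correction in Section 12, which also names a paired test for the two diet groups.
- Report 80% power for 1.63 SD with 7 per arm and 2.02 SD with 5 completers per arm, with 95% CI half-widths of 1.16 and 1.46 SD. Power of 14%, 28% and 41% at 0.5, 0.8 and 1.0 SD with 7 per arm may be added if labelled as assumed scenarios.
- Plan to estimate the SD of irisin change in these women, with its confidence interval, for the follow-on grant.

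Reconcile Section 4, where irisin is the primary outcome for sizing, with Section 11, where hand-grip strength is primary and irisin secondary. If irisin stays secondary, say plainly that the size was not derived for the primary endpoint.

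The cost is rewording. No further women, visits or samples are needed. The stated sensitivity becomes less favourable, but it can be defended.

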- 24-hs food and physical activity questionnaire
- Seated resting blood pressure will be measured.
- Weight will be measured.
- Subjects will take the assigned supplement.
- Venous blood samples will be collected (20 ml).
- A hematocrit will be performed in order to discard anemia.
- Snack will be provided to the participants.
- Hand grip strength and SPPB test will be completed.
- Unused and empty packages of the study product will be return.

10) Study Timelines

Duration of individual subject's participation will be ~6 weeks. The study will include: 1 visit (visit 0) for the screening process that will last approximately 2 h and 3 more visits (visits 1, 2 and 3) for intervention process that will last approximately 2 h each. Visit 0 will involve an in-person screening to obtain written informed consent and determine if subjects meet the inclusion/exclusion criteria. Visit 1, 2 and 3 (at 0, 3 weeks and at the end of the 6 weeks, respectively) will include blood sample collection and tests performance.

11) Study Endpoints

Primary endpoint:

Hand-grip strength media value of 16 kg or lower

Secondary endpoints:

Levels of Irisin as a marker of sarcopenia

Glucose, Insulin, GLP-1, GLP-2, GIP, Adiponectin, leptin and ghrelin, Blood urea nitrogen, creatinine, Aspartate transaminase, Alanine transaminase, Total cholesterol, triglyceride, high-density lipoprotein (HDL), low-density lipoprotein, IL-6, IL-15, 25-hydroxyvitamin D as markers of general metabolism state.

12) Data and/or Specimen Management and Confidentiality

Data management: The de-identified data will be analyzed for statistical significance with the help of the Biostatistics group at UC Davis, including univariate graphical, analytic summaries and bivariate relationships using box plots, scatter plots, and correlations. To compare participants in the two diet groups (Placebo control and freeze-dried table grape powder) a paired Student's t test (two-tailed) will be used. Data involving more than two repeated measures, such as grip strength tasks, or irisin levels, will be assessed by repeated measures (ANOVA). Differences will be considered significant at $P < 0.05$. Significant results will be also subjected to analysis of covariance (ANCOVA) to account for group differences at baseline and post hoc comparisons using the Bonferroni correction.

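### The 80% power in Section 4 is for one irisin t-test at 0.05, not for the repeated-measures ANOVA with Bonferroni follow-up that Section 12 assigns to irisin

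*Protocol*

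**What the plan says.** Protocol Section 4 (Enrollment Numbers) takes change in plasma irisin "as our primary outcome to determine the power calculations for sample size". It states that "5 individuals per group are required to reach 80% power to detect differences in irisin levels between the groups" at alpha 0.05, "using a two-sided paired T-test". The two extra women per arm are explained only by attrition: "We propose to enroll 7 individuals per group, instead of 5, in the event of a patient drop out of the study". The effect and its SD are not given; the text refers to earlier preliminary data.

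Protocol Section 12 (Data management) first says that, for comparing the two diet groups, "a paired Student's t test (two-tailed) will be used". It then names irisin for another method: "Data involving more than two repeated measures, such as grip strength tasks, or irisin levels, will be assessed by repeated measures (ANOVA)". Significance is set at P<0.05. Results that are significant go on to ANCOVA "to account for group differences at baseline and post hoc comparisons using the Bonferroni correction". The number of post hoc comparisons is not given. Irisin is measured at visits 1, 2 and 3 (weeks 0, 3 and 6; Sections 9 and 10).

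**The concern.** A power statement holds for one test at one alpha. Section 4 has one test at 0.05. The irisin route in Section 12 has an omnibus test over three visits, and then specific comparisons at 0.05 divided by an unstated number.

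The omnibus test can show that the two arms have different time profiles. It does not show at which visit they differ or in which direction. The hypothesis in Section 2 is directional (grape powder raises irisin), so the comparison that speaks to it is the one at the reduced alpha.

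Two things are at stake. The only power figure in the protocol may not describe the planned analysis. And the step from 5 to 7 per arm, presented as cover for drop-out, may be needed in part or in full to pay for the correction. Section 13 lists several reasons for removal, so some loss is plausible.

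This is separate from the use of a paired test for two randomised groups. It remains if an independent-groups test is substituted.

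**Working it through.** **Inputs from the protocol.** 5 per group, 80% power, two-sided alpha 0.05; 7 per group enrolled; three irisin measurements; ANOVA at P<0.05, then Bonferroni.

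**Assumed, because the protocol does not say.** Effect and SD; number of comparisons (two = change at weeks 3 and 6; three = three visits or three pairs of visits); group-by-time as the ANOVA effect of interest; equal variances and correlations across visits, with the SD of change set to 1; week-3 effect at 0, 50 or 100% of the week-6 effect.

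**Step 1: the plan's own figure.** It cannot be reproduced without an effect and SD, so the effect is back-solved. For two independent groups, power follows the noncentral t with 2n−2 df and noncentrality δ = d√(n/2). With n = 5, 8 df and critical t 2.306, power is 0.800 at d = 2.02 (δ = 2.024 × √2.5 = 3.20).

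**Step 2: same effect, single week-6 contrast at the corrected alpha.**

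| n per arm | δ | alpha 0.05 | 0.05/2 | 0.05/3 |
|---|---|---|---|---|
| 5 | 3.20 | 80.0% | 67.3% | 59.2% |
| 6 | 3.51 | 88.4% | 79.2% | 72.6% |
| 7 | 3.79 | 93.5% | 87.2% | 82.4% |

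Taking the paired calculation at face value (dz = 1.68, n = 5, 4 df) gives 63.0% at 0.05/2 and 52.3% at 0.05/3.

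**Step 3: the ANOVA step alone, at 0.05.** Noncentral F with 2 and 2(2n−2) df, and λ = (n/2) Σ(v − v̄)² / 0.5, where v is the group difference at weeks 0, 3 and 6. For n = 5 the df are 2 and 16.
- Week-3 effect 0 or 100% of week 6: Σ = (2/3)d² = 2.73, λ = 2.5 × 2.73 / 0.5 = 13.7, power 86%.
- Week-3 effect 50%: Σ = d²/2 = 2.05, λ = 2.5 × 2.05 / 0.5 = 10.2, power 74%.

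**Step 4: the two-step route.** Group-by-time P<0.05 and then the week-6 change contrast at the Bonferroni level, simulated with at least 20,000 trials per setting. The ranges cover the three week-3 patterns; repeat runs agree within about one percentage point.

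| n per arm | two comparisons | three comparisons |
|---|---|---|
| 5 | 64–67% | 57–59% |
| 6 | 76–78% | 71–72% |
| 7 | 85–87% | 81–82% |

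**Step 5: sensitivity to the back-solved effect.** If 5 is merely the smallest n that reaches 80%, the effect could be anything from d = 2.02 up to d = 2.38, where 4 per group would already suffice. At d = 2.38 the two-step route at 5 per arm has 80–82% (two comparisons) or 74–75% (three). At 6 per arm it has about 90–91% or 86–87%.

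**Step 6: sensitivity to the number of comparisons.** With six comparisons and d = 2.02, the single contrast has 45% at 5 per arm and 72% at 7.

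**The case against.** The best reply is that Bonferroni does not decide whether irisin is called significant. Section 12 sets significance at P<0.05 and sends only results that are already significant to post hoc comparison. At 5 per arm the ANOVA alone has 74–86% power, above the printed 80% in two of the three time patterns. This stands. The loss arises at the specific corrected contrast, not at the omnibus test, and no sentence says that the group difference is declared at 0.05/3.

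Section 12 also keeps a t-test for comparing the two groups, and change in irisin, with one value per woman, would fit it. That makes the text ambiguous but does not resolve it, because the next sentence names irisin for ANOVA. An analysis plan that is not shown might settle the order of the tests, but the two statements that disagree both stand in the protocol.

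A reader might infer that irisin power is only about 58%. The documents do not support that as a flat figure. It needs three comparisons, an independent-groups test, 5 completers per arm and the smallest effect compatible with the sample size.

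A reader might also infer that the Bonferroni step always consumes the whole drop-out allowance, or that losing one woman per arm must put power below 80%. At d = 2.02 with two or three comparisons, 6 per arm does fall below 80%. At d = 2.38 it does not.

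Finally, this is a self-described pilot, and Section 11 lists irisin as secondary. That conflict with Section 4, like the paired test, is a larger problem in the same sections. Both limit the weight of this point but do not remove it, since the sample size rests on irisin.

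**Conclusion.** The concern holds in a conditional form. The 80% in Section 4 is the power of one t-test at 0.05. Section 12 assigns irisin to repeated-measures ANOVA with Bonferroni-corrected follow-up, and the protocol gives no power for that route and no inputs from which to derive it.

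If the effect is back-solved to exactly 80% at 5 per group, the route to a week-6 difference loses roughly 13 to 23 percentage points at that size (80 − 67 to 80 − 57) with two or three comparisons. Most or all of the two-per-arm margin then goes to the correction. At the largest effect still compatible with n = 5, the route has about 80–82% or 74–75%, so the shortfall from 80% is small or absent.

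This does not show that the trial is underpowered as enrolled. If all 7 per arm complete, the route meets 80% with two or three comparisons under the back-solved effect; with more comparisons it may not. The defect is a power claim attached to the wrong analysis, with an uncertain drop-out margin.

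**What to change.** In Section 12, name one decision test for irisin: the grape-versus-placebo difference in change from visit 1 to visit 3, by an independent-groups comparison at two-sided 0.05. State that it is not gated by the omnibus ANOVA and not Bonferroni-corrected, and that the week-3 and other contrasts are supportive. In Section 4, restate the power for that test with its effect and SD. At d = 2.02 it would be 80% with 5 per arm, 88% with 6 and 93.5% with 7, so the two extra women per arm would again be a true drop-out margin.

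If the ANOVA-then-Bonferroni route is kept, state the number of comparisons and replace the 80% with the power of that route at the number of women expected to complete.

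The change is wording in two sections, with no added women, visits or assays. The price is that the week-3 irisin contrast becomes supportive or, if the route is kept, that the stated power is less favourable.

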Exclusion Criteria: history of specific muscle diseases, peripheral vascular disease, intermittent claudication, central and peripheral nervous system disorders, cachexia, active diagnosis of diabetes mellitus, myocardial infarction, stroke, liver disease, on dialysis or long-term steroid therapy, and/or actively receiving treatment for cancer or severe infection (excluding short-term antibiotic therapy), weight less than 140 pounds, anemia and blood donations in the past 30 days. In addition, participants should not be taking dietary supplements at the time of the study.

6) Recruitment Methods

We will recruit by: 1) posting flyers on campus bulletin boards; 2) listing the study on our departmental website that provides a list of all current departmental trials; 3) listing the study on campus list servers; 4) advertising in the local newspapers and 5) posting on social media. All recruitment material will use similar language and list a study office phone number, clinical coordinator email and the departmental website for clinical trials (**Attachment A**). Respondents will be contacted by phone and pre-screened. Information about the study will be provided during the phone interview (**Attachment B**). For subjects that are eligible and interested in enrolling in the study, an in-person screening visit 1 appointment will be scheduled with the investigator or designee and the informed consent form emailed to them in advance. If the participants meet all the inclusion criteria, in the same visit the investigator or designee will review the informed consent form with the subjects, explain the study to the subjects and answer any questions prior signing the consent. Only once the informed consent form is signed, a diet history questionnaire (**Attachment C**) will be completed by the subjects.

7) Compensation to the Subjects

Subjects will be compensated at a rate roughly proportional to the inconvenience

incurred according to the following schedule:

- Visit 0 (screening): \$50 for inconvenience
- Visit 1: \$75 for inconvenience
- Visit 2: \$75 for inconvenience
- Visit 3: \$75 for inconvenience + \$50 for study completion

Subjects will be paid at the completion of their involvement in the study. The total compensation that a participant might earn is \$325 for completion of all visits. Subjects that withdraw from the study early will be compensated based on the visit(s) they completed.

8) Screening procedures to determine eligibility:

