- The person in charge of the test will read grip strength in kilograms from the outside dial and record the result to the nearest 1 kg on the data entry form.
- The person in charge of the test will ask the participant to repeat measurement in the left hand.
- The participant will be asked to repeat two further measurements for each hand alternating sides to give three readings in total for each side.
- The best of the 3 grip strength measurements will be used in statistical analyses to encourage the subjects to get as high a score as possible.
- The person in charge will also record hand dominance, i.e. right, left or ambidextrous (people who can genuinely write with both hands).

For those participants that meet the previous inclusion criteria the following parameters will be explored:

1. Seated resting blood pressure.
2. Weight and height.

3. A finger stick blood sample (~1-2 drop equal to ~ 100ul) will be collected to confirm that subjects meet the inclusion criteria for fasting levels of blood glucose and cholesterol, plus a hematocrit to discard anemia.

Briefly, at Visit 0 (screening visit):

- Subjects will arrive fasted for at least 12 h prior to this visit (water ok).
- Informed consent will be obtained.
- ID number will be assigned.
- Hand grip strength test will be conduct.
- Seated resting blood pressure will be measured.
- Weight and height will be measured.
- A finger stick blood sample (~1-2 drop equal to ~ 100ul) to confirm that subjects meet the inclusion criteria (glucose, cholesterol and hematocrit).
- Diet history questionnaire (**Attachment C**) will be completed by the subjects to review medical history (including known positivity test for COVID-19), concomitant medications (including COVID-19 immunization dates), inclusion and exclusion criteria.
- This visit will take approximately 2 h to complete

9) Procedures Involved

Schedule of procedures

	Visit 0 Screening	Visit 1 Baseline	Visit 2 3-weeks visit	Visit 3 6-weeks final visit
Informed consent	X			
Inclusion / Exclusion criteria	X			
Review medical history	X			
Review concomitant medications	X		X	
Height, weight and blood pressure	X	X	X	X
Finger stick		X	X	X
Hand grip strength test	X	X	X	X
SPPB test		X	X	X

Blood draws for plasma determinations	X	X	X	X
Hematocrit	X	X	X	X
Study product randomization		X		
Study product intake			X	X
Dispense study product for home		X	X	
Return unused study product and empty packages			X	X
Dispense stool and urine collection kit		X	X	

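### The 140-pound weight exclusion and the BMI range of 18.4-24.9 together admit no woman shorter than about 160 cm, so the trial can enrol a much narrower BMI range than it states

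*Protocol*

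**What the plan says.** Protocol section 5 (Inclusion and Exclusion Criteria) defines the target group as "postmenopausal women aged 60 years or older" who also have low grip strength ("hand-grip strength media value of 16 kg or lower"), a BMI described as normal and given as 18.4 to 24.9 kg/m², and limits on blood pressure, glucose and cholesterol.

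The exclusion list in the same section contains "weight less than 140 pounds". It stands next to anaemia and recent blood donation; cachexia is listed separately.

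Section 8 (Screening procedures) confirms that both rules are checked on the same woman at visit 0: "Weight and height will be measured". No height criterion appears anywhere. No reason is given for the weight floor, and nothing says that it is meant to narrow the BMI range. The enrolment target in section 4 is small: "In total we will have 14 subjects".

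**The concern.** BMI already ties weight to height. A fixed weight floor placed on top of a BMI ceiling therefore acts as an unstated minimum height, and it raises the effective lower BMI limit for every woman who is not very tall. If the floor lies high relative to the BMI range, the trial describes one population and can enrol another.

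Two things are at stake. The first is recruitment: the floor is added to limits on grip, blood pressure, glucose, cholesterol and supplement use. The second is applicability: a result reported for postmenopausal women of normal BMI would contain no one under the implied height and, at common heights, only women in the upper part of the range. Section 2 says the pilot is to support an application for a larger study, so an undescribed restriction could be carried forward.

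**Working it through.** The protocol states no figure for the combined effect of the two rules, so there is none to reproduce. The first two steps use only the protocol's own numbers; the third needs assumptions.

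**Inputs (section 5).** Weight floor 140 lb = 140 × 0.45359 = 63.50 kg. BMI limits 18.4 and 24.9 kg/m², a width of 6.5.

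**Step 1. Heights at which the floor meets each BMI limit.** Height = √(weight / BMI).
- Upper limit: √(63.50 / 24.9) = 1.597 m. Any shorter woman who weighs 140 lb has a BMI above 24.9, so she fails one rule or the other.
- Lower limit: √(63.50 / 18.4) = 1.858 m. Below this height the weight floor, not the BMI of 18.4, sets the lower bound.

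**Step 2. BMI window left open at a given height.** Effective lower BMI = 63.50 / height². Share of the stated width = (24.9 − effective lower BMI) / 6.5.

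| Height | Effective lower BMI | Open window | Share of stated width |
|---|---|---|---|
| 155 cm | 26.4 | none | 0% |
| 160 cm | 24.81 | 24.8-24.9 | 1% |
| 162 cm | 24.20 | 24.2-24.9 | 11% |
| 165 cm | 23.33 | 23.3-24.9 | 24% |
| 168 cm | 22.50 | 22.5-24.9 | 37% |
| 170 cm | 21.97 | 22.0-24.9 | 45% |
| 175 cm | 20.74 | 20.7-24.9 | 64% |

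In pounds, the BMI rule alone allows 103.8-140.5 lb at 160 cm and 110.4-149.5 lb at 165 cm. With the floor added these become 140-140.5 lb and 140-149.5 lb.

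**Step 3. Share of women with BMI 18.4-24.9 who are excluded by the floor.** This is the probability that BMI × height² is below 63.50. The protocol gives no distribution of height or BMI, so both are assumed: normal heights with SD 6-7 cm, and three shapes for BMI inside the stated range. The shares come from simulation with 400,000 women per setting.

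| Assumed mean height | BMI uniform over 18.4-24.9 | BMI weighted to the top (triangular) | All BMI in 22.5-24.9 (extreme) |
|---|---|---|---|
| 156 cm | 94-96% | 90-92% | 85-88% |
| 160 cm | 87-89% | 79-81% | 69-72% |
| 162 cm | 82-83% | 71-73% | 59-61% |
| 164 cm | 76-77% | 63-64% | 48-49% |
| 166 cm | 70% | 55% | 36-38% |

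With uniform BMI the excluded share falls below half only at a mean height of about 172 cm or more.

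**The case against.** The strongest reply is that there is no contradiction. Inclusion and exclusion criteria are meant to act jointly, and every exclusion narrows the included group. A woman of about 160 cm or taller can meet both rules, and the BMI ceiling still binds. This stands: the two lines can be satisfied together, and only the lower BMI limit is displaced. It does not explain why the section states a range whose lower end is out of reach below about 186 cm.

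The second reply is that the floor may be a precaution for blood drawing. It sits beside anaemia and recent donation, and the trial takes 20 mL at each of three visits. That is a fair inference, and it means the floor cannot be dismissed as redundant merely because BMI and cachexia already deal with underweight. But the protocol does not say so, and section 14 presents the total of about 60 mL as acceptable for healthy adults without any weight condition.

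The third reply is that the consequences are limited. This is a pilot, randomisation is unaffected, and no accrual rate or catchment size is given, so the risk to enrolling 14 women cannot be sized. This also stands.

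A reader might infer more than the documents support:
- That the floor removes most normal-BMI women as a matter of fact. This depends on the assumed distributions in step 3 and fails at the extreme settings.
- That only tall women can enter. The threshold of 159.7 cm lies near the assumed mean heights: with a mean of 162 cm and SD 6-7, about 63-65% of women exceed it.
- That a low-grip criterion selects smaller women, whom the floor then removes. Nothing in the protocol speaks to this.

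**Conclusion.** The point holds as a mismatch between the stated and the achievable population. From the protocol's own two numbers, no woman under about 160 cm can be enrolled, the BMI limit of 18.4 is inoperative below about 186 cm, and at 165 cm about three quarters of the stated BMI width is closed (100% − 24% = 76%). These results need no outside figure.

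The share of normal-BMI women excluded is conditional. For assumed mean heights of 156-164 cm (SD 6-7) it is about 76-96% with uniform BMI and 63-92% with BMI weighted to the top of the range. Within those heights it falls to about half only if all BMI lies in 22.5-24.9 and mean height is 164 cm; taller assumed populations bring it lower.

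The effect is on recruitment and applicability. It does not bias the comparison of grape powder with placebo and does not touch the analysis. It should be corrected before enrolment, but it does not invalidate the design.

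**What to change.** Reconcile the two lines of section 5 before enrolment, in one of two ways:
- align the weight criterion with the stated BMI range, so that the range given is the range that can be enrolled; or
- if the floor serves a safety purpose, state that purpose, and restate the BMI and height range it implies as the trial population, there and wherever results are described.

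Which route to take, and any value, is for the investigator.

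The cost is an edit to the eligibility text, and section 1 describes this as a new submission. The first route also requires the investigator to confirm that the blood volume is acceptable for the women it would admit. The second leaves recruitment as narrow as it is now but makes the restriction visible.
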